4.6 Medical History

Medical history will be coded using Medical Dictionary for Regulatory Activities (MedDRA[®]), Version 25.1 and assigned to a System Organ Class (SOC) and Preferred Term (PT).

Medical history data will be summarized by study day treatment, and overall for the SP and listed by participant including visit, description of the disease/procedure.

4.7 Prior and Concomitant Medication

Prior and Concomitant Medication:

Medications will be considered as prior if the start date of the medication is before the date of first administration of the study drug.

Medications will be considered as concomitant if they are taken at least once in the treatment period starting with the first study administration and ending after the last study drug administration during the study.

Medications starting prior to first administration of study drug and continuing during the study visit will be considered both prior and concomitant medication.

A summary table and by-participant listings of prior and concomitant medications will be provided for the SP.

4.8 Treatment Exposure and Compliance

4.8.1 Treatment Exposure

A by-participant listing of participant exposure to DCR-AUD will be generated. The listing will include dose, date and time, unit, formulation, route, and frequency.

4.8.2 Compliance

Compliance(%) = $100 \times \text{Total volume delivered (mL)}/\text{Total volume planned (mL)}$

A by-participant listing of treatment compliance will be provided.

4.9 Analysis Supporting Primary Objective(s)

Not Applicable.

4.10 Analysis Supporting Secondary Objective(s)

Not Applicable.

4.11 Efficacy Evaluation

Not applicable.

4.12 Pharmacokinetic Analysis, Concentration, and Parameter TFLs, and Statistical Analysis of Pharmacokinetic Parameters for Final Analysis

4.12.1 Pharmacokinetic Concentrations

Concentration Listings:

Pharmacokinetic concentration data for DCR-AUD, will be listed by study days, nominal and actual timepoints and participant for the SP. Concentration listings will include nominal PK sampling time, actual sampling times relative to dose administration, deviation from nominal time, and percent deviation from nominal time, and concentrations. Plasma concentrations below the lower limit of quantification (LLOQ) will be presented as below the limit of quantification (BLQ) in the listings and the LLOQ value presented as a footnote. Missing PK samples will be reported as no sample (NS) or not reportable (NR) as appropriate and considered excluded from PK analysis.

Concentration Summary Tables:

Source data as reported from the laboratory will be used for calculation of concentration summary statistics. Tabular summaries for concentration-time data will report N (number of participants who received treatment), n (number of participants with non-missing values), and n(BLQ) (the number of participants with BLQ samples).

Concentration for DCR-AUD will be summarized by study days, and nominal timepoint for the PKP. The following descriptive statistics will be presented for plasma concentrations obtained at each nominal time point: N, n, n(BLQ), arithmetic mean, SD, coefficient of variation (CV%), geometric mean, geometric CV% (calculated as: $gCV\% = \text{SQRT}(e^s - 1) * 100$; where s is the SD of the log-transformed values), median, minimum, and maximum values.

For summary tables, all BLQs will be considered zero, and the number of BLQs and non-BLQs at each scheduled time point will be reported. Summary Statistics will not be calculated if non-BLQ concentrations at a scheduled time point is <3 and will be reported as NC.

The rules followed for calculation and presentation of concentration data with regards to the number of decimal places/significant digits for the listings of participant level concentrations and summary tables of concentration are as follows:

Concentration Listings and Tables	Rounding
Individual concentrations	n s.f. as supplied by bioanalytical laboratory
Minimum and Maximum	n s.f. at 3
Mean/SD/Median/Geomean	n s.f. at 3
CV%/gCV%	n s.f. at 3
N/n	Whole number

s.f = significant figures, d.p. = decimal place

Concentration Figures:

For arithmetic mean linear/linear graphs, all BLQ values will be substituted with zero for calculation of arithmetic mean and for log/linear graphs the log transformed arithmetic mean will be displayed (this should not include zero).

For individual linear/linear and log/linear graphs all BLQ values will be substituted as follows:

- BLQs at the beginning of a participant profile (i.e., before the first incidence of a measurable concentration) will be assigned to zero. When using log/linear scale, these timepoints will be considered missing.
- BLQs at the end of a participant profile (i.e., after the last incidence of a measurable concentration) will be set to missing.
- Single BLQs which fall between two measurable concentrations will be set to missing.
- Consecutive BLQs which fall between measurable concentrations will be set to missing. Measurable concentrations after consecutive BLQs will be set to missing.

To visualize participant-level concentrations and the comparison between study days, the descriptive PK graphs listed below will be generated Including LLOQ line in individual and summary plots.

- Figure x.x.x: Individual participant profiles for DCR-AUD Plasma Concentration Time Data by Study Day – (Linear Scale and Semi-Logarithmic Scale) (SP)
- Figure x.x.x : Overlaid individual participant profiles for DCR-AUD Plasma Concentration Time Data by Study Day – (Linear Scale and Semi-Logarithmic Scale) (SP)
- Figure x.x.x : Mean (\pm SD) DCR-AUD Plasma Concentration Time Data by Study Day – (Linear Scale and Semi-Logarithmic Scale) (PKP)

Figures will be generated in color using unique line style and marker for each plot in the graph. For all PK concentration-time plots, linear scale will be used for x-axis (e.g., do not use an ordinal scale).

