9.4.3.3. Pharmacokinetics

Plasma concentrations and PK parameters will be listed and summarized by group and by time point with descriptive statistics. The arithmetic mean, SD, CV%, geometric mean, geometric CV%, minimum, median, and maximum will be presented.

Additional PK parameters may be estimated if deemed appropriate. Details will be provided in the PK Analysis Plan. Analysis of PK parameters may be reported in a supplement to the CSR.

PK analyses will be conducted with noncompartmental and/or compartmental models to determine PK parameter estimates. Population PK and Population PK-PD analyses may be performed and will be reported in a separate report.

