Biostatistics group will consider the derived PK parameters as source data and will use this data without rounding for calculation of PK parameters summary statistics tables.

PK parameters will be summarized by study day with descriptive statistics for the PKP.

Tabular summaries for PK parameters will report N (number of participants who received treatment) and n (number of participants with non-missing values).

Descriptive statistics for calculated PK parameters will include N, n, arithmetic mean, SD, CV%, geometric mean, gCV%, median, minimum, and maximum values. For t_{max} , only N, n, median, minimum, and maximum values will be presented. No descriptive statistics will be determined when fewer than three individual PK parameters are available.

The rules followed for presentation of PK parameters data with regards to the number of decimal places/significant digits for the listings of participant level PK parameters and summary tables of PK parameters are as follows:

PK Parameter Listings and Tables	Rounding
Derived Individual parameters	3 s.f.
Directly Derived Individual parameters (C _{max} , C ₁₂ , C ₂₄)	n s.f. as supplied by the analytical laboratory but not more than 3 s.f.
Minimum and Maximum	3 s.f.
Mean/SD/Median/Geomean	3 s.f.
CV%/gCV%	3 s.f.
Comparative estimates (e.g. ratios)	3 s.f.
CI and other percentages	2 d.p.
p-values	4 d.p.
N/n	Whole number
Exceptions for PK Tables	
t_{max} individuals and min/max	3 s.f.
t_{max} median only	3 s.f.

s.f = significant figures, d.p. = decimal place

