Individual participant's biomarker (acetaldehyde, acetate, and ethanol) plasma concentration values (baseline unadjusted values only) will be provided by [REDACTED] Laboratories and [REDACTED]. Baseline unadjusted and adjusted acetaldehyde, acetate, and ethanol concentration values will be listed by study day, timepoint, ALDH2 mutation, and participant for the PP by [REDACTED]. Concentration listings will include nominal biomarker sampling time, actual sampling times relative to dose administration, and percentage change from baseline. The corresponding baseline for each timepoint will be taken on Day -1. For the biomarker concentration summary tables, descriptive statistics (N, n, arithmetic

mean, SD, CV%, geometric mean, gCV%, median, IQR (inter quartile range), minimum, and maximum values) will be presented by study day, nominal timepoint, EIA days, and ALDH2 mutation. For time variables only median, T_{min} and T_{max} will be presented. A by participant listing of ALDH2 mutation will be provided.

To visualize the comparison between study days the descriptive biomarker graphs will be generated.

- Figure x.x.x: Individual Participant Profiles for acetaldehyde, acetate, and ethanol, Plasma Concentration Time Data (Unadjusted and Adjusted for Baseline) by study day and EIA day (SP)
- Figure x.x.x: Overlaid Individual Participant Profiles for acetaldehyde, acetate, and ethanol Plasma Concentration Time Data (Unadjusted and Adjusted for Baseline) by study day and EIA day (SP). The profiles for ALDH2 mutation will be plotted with dotted lines.
- Figure x.x.x: Mean (\pm SD) baseline adjusted acetaldehyde, acetate, and ethanol Plasma Concentration Time Data by study day and EIA day (PP)
- Figure x.x.x: Mean (\pm SD) baseline adjusted acetaldehyde, acetate, and ethanol Plasma Concentration without ALDH2 Mutant Time Data by study day and EIA day (PP)
- Figure x.x.x: The Mean (\pm SD) baseline unadjusted acetaldehyde, acetate, and ethanol Plasma Concentration Time profiles by study day and EIA days (PP)
- Figure x.x.x: The Mean (\pm SD) baseline unadjusted acetaldehyde, acetate, and ethanol Plasma Concentration without ALDH2 Mutant Time profiles by study day and EIA days (PP)

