4.12.5 Pharmacodynamic Parameters

DCR-AUD is designed to selectively reduce ALDH2 levels in the liver and the conversion of acetaldehyde to acetic acid. The build-up of acetaldehyde causes unpleasant effects after drinking (e.g., headache, facial flushing, tachycardia, nausea, vomiting). As such, the PD activity of DCR AUD will be assessed during EIAs using blood biomarkers (alcohol, acetaldehyde, and acetate), assessment of 6 symptoms and their severity induced during EIAs, and objective physiological biomarkers (heart rate and facial skin temperature). Participants' subjective experience of the effects

of alcohol will be assessed. Instructions for the collection and handling of biological samples will be provided by the Sponsor in the Laboratory Manual and the Laboratory Specification document.

PD parameters will be calculated using drug effect model from the biomarker time data using Phoenix® WinNonlin® 8.3 or higher. The biomarker parameters alcohol, acetaldehyde, and acetate unadjusted and adjusted for baseline will be estimated for treatment, nominal point, EIA days, and ALDH2 status. The Phoenix WinNonlin project file including all settings and analysis input file will be transferred to Dicerna when the biomarker PD analyses are completed.

The unadjusted and adjusted biomarker parameters will all be listed, and unadjusted parameters will be summarized by time point and treatment. Descriptive statistics (number, arithmetic mean, SD, CV%, geometric mean, gCV%, minimum, median, and maximum) will be presented by nominal points, treatment, ALDH2 status, and EIA days for absolute, and percentage change from the biomarker baseline, where appropriate. For time variables Tmin and Tmax, only median will be presented.

One way ANOVA model will be used to compare the unadjusted Biomarker parameters for DCR-AUD and Placebo for PP.

To visualize the comparison between treatment and placebo following alcohol consumption the following descriptive PD parameter graphs will be generated:

The mean (\pm SD) Cmax and AUC0-4h of acetaldehyde, acetate, and ethanol will be plotted with EIA days. Two mean Cmax figures will be prepared: one in μ M and another in ng/mL units.

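### Setting BLQ to zero leaves geometric mean and gCV% undefined at concentration time points with some BLQ values, and the percent-change rows of SAP Table 4-2 divide only the Day -1 term; two further formulas need checking against the PDF

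*SAP*

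**What the plan says.** **Concentration tables (SAP 4.12.1).** Arithmetic and geometric statistics are required at each nominal time point. On BLQ values: "For summary tables, all BLQs will be considered zero, and the number of BLQs and non-BLQs at each scheduled time point will be reported". The only suppression rule is: "Summary Statistics will not be calculated if non-BLQ concentrations at a scheduled time point is <3 and will be reported as NC".

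**Other BLQ rules.** For mean figures, SAP 4.12.1 says "for log/linear graphs the log transformed arithmetic mean will be displayed (this should not include zero". SAP 4.12.2 sets some BLQs to missing or to LLOQ/2, but only for deriving PK parameters. Neither rule is extended to the concentration tables.

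**gCV%.** SAP 4.12.1 gives 100*SQRT(e^s - 1), "where s is the SD of the log-transformed values". It is the SAP's only gCV% formula. The statistic is also required for:
- PK parameters (SAP 4.12.2: "Descriptive statistics for calculated PK parameters will include N, n, arithmetic mean, SD, CV%, geometric mean, gCV");
- biomarker concentrations (SAP 4.12.4: "mean, SD, CV%, geometric mean, gCV%, median, IQR (inter quartile range), minimum, and maximum values");
- biomarker parameters (SAP 4.12.5: "Descriptive statistics (number, arithmetic mean, SD, CV%, geometric mean, gCV%, minimum, median, and maximum) will be presented by nominal points").

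For plasma concentrations and PK parameters the requirement comes from Protocol 9.4.3.3: "The arithmetic mean, SD, CV%, geometric mean, geometric CV%, minimum, median, and maximum will be presented".

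**Table 4-2 (SAP 4.12.4).** Cav is described as an average over 0 to 4 h but equated to AUC0-4h. The percent-change rows for AUC0-4h, Cav and Cmax all have the form ((Day X - Day -1/day -1)) x 100. Table 3-1 (SAP 3.2.5) defines Cav as an average and the percent change as relative to the Day -1 level.

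**The concern.** The zero rule and the geometric statistics cannot both be followed where a time point mixes BLQ and quantifiable values, because the log of zero does not exist. Each programmer must then choose: return 0, return missing, or drop the zeros without saying so. The three choices give different tables.

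The percent-change rows fail a basic test: with no change from Day -1 they do not return zero.

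The printed gCV% formula puts the SD of the logs where the lognormal result needs the variance. The printed Cav is an area, not an average.

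At stake are the accuracy and reproducibility of tables serving the secondary PK and plasma PD objectives.

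**Working it through.** **Inputs.** Twelve active participants are planned (SAP 4.20). BLQ = 0, and NC applies below 3 non-BLQ values (SAP 4.12.1). The documents give no LLOQ, BLQ rate or log-scale SD, so those are assumed below and shown as ranges. The plan states no figure to reproduce.

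**1. Where the zero rule fails.** For k BLQ of 12:
- k = 0: no zeros, all statistics computable.
- k = 1 to 9: at least 3 quantifiable, so not NC. The mean log is minus infinity, so the log-form geometric mean and gCV% are undefined. The product form gives 0.
- k = 10 to 12: fewer than 3 quantifiable, so NC.

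If each sample is BLQ independently with probability p, the chance that a time point has k = 1 to 9 is:

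| p | 5% | 10% | 25% | 50% | 75% | 90% |
|---|---|---|---|---|---|---|
| chance | 46% | 72% | 97% | 98% | 61% | 11% |

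**2. What dropping the zeros does.** Take an illustrative time point with 5 BLQ and the values 2, 3, 4, 5, 6, 8, 10.
- Zero-filled arithmetic mean: 38/12 = 3.17 (n = 12).
- Geometric mean of the non-BLQ values: 57600^(1/7) = 4.79 (n = 7).

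A geometric mean above the arithmetic mean looks impossible unless the two denominators are shown. Assuming lognormal quantifiable values, the ratio of the two is about [12/(12-k)]*exp(-s^2/2):

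| | s = 0.3 | s = 0.5 | s = 1.0 |
|---|---|---|---|
| k = 1 | 1.04 | 0.96 | 0.66 |
| k = 5 | 1.64 | 1.51 | 1.04 |
| k = 9 | 3.82 | 3.53 | 2.43 |

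**3. Percent-change rows.** Write D for the Day -1 value and X for the Day X value, and read the divisor as the Day -1 value. The printed form is 100*(X - D/D) = 100*(X - 1). The intended form is 100*(X - D)/D.

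| D, X (illustrative) | literal | intended |
|---|---|---|
| 20, 25 | 2400 | 25 |
| 20, 20 | 1900 | 0 |
| 0.5, 0.625 (first pair, unit 40 times larger) | -37.5 | 25 |

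The literal result depends on the unit, while Table 3-1 asks for Cmax in two units.

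**4. gCV%, if the PDF reads the same.** Printed 100*SQRT(exp(s) - 1); standard 100*SQRT(exp(s^2) - 1).

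| s | 0.3 | 0.5 | 1.0 | 1.5 |
|---|---|---|---|---|
| printed | 59.1 | 80.5 | 131.1 | 186.6 |
| standard | 30.7 | 53.3 | 131.1 | 291.3 |

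The printed form overstates below s = 1, agrees at s = 1 and understates above it. For the seven values in step 2, s = 0.5585, giving 86.5 printed and 60.5 standard.

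**5. Cav, if the PDF reads the same.** The time average is AUC0-4h / 4 h. Without the divisor, Cav and Cav-adjusted are 4 times too large and carry AUC units.

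**The case against.** **The formulas may have been damaged in reading.** The text here is machine-read from the PDF. The gCV% error is one missing superscript, and s defined as the SD is exactly what a formula with s^2 needs. The Cav error is one missing divisor. Neighbouring formulas in Table 4-1 also look odd: AUC0-x is set equal to itself, and CL/F ends in a stray division by F. This stands, so both corrections are conditional on the PDF. It is much weaker for the percent-change rows, where the same bracket recurs three times. The AUC0-inf and %AUCex formulas came through intact.

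**The labels settle the intent.** Each row is named a percent change from Day -1, Table 3-1 agrees, and SAP 4.12.5 has the PD parameters calculated in Phoenix WinNonlin, for which Table 3-1 gives Cav an output name. This stands. The sizes in steps 3 and 5 arise only if someone programs the formula literally against its label.

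**A sensible programmer would drop the zeros, as the figure rule does.** Partly so. That rule covers only mean log/linear graphs, and dropping the zeros still leaves the unequal denominators unexplained.

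**Using non-BLQ values only is one convention among several.** This stands. It describes only measurable participants and creates the contrast in step 2. Reporting NC whenever any value is BLQ is also acceptable.

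**Conclusion.** The BLQ conflict is in plain prose and holds whatever the PDF formulas show. It affects only time points with 1 to 9 BLQ of 12, and how many there will be is unknown. A reader might infer that the geometric statistics cannot be computed in these tables at all. The documents do not support that: time points without BLQ are fine, those with 10 or more are NC, and the arithmetic mean, SD, median, minimum and maximum can be computed with zeros.

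The percent-change rows are wrong as bracketed, but their meaning is clear from their labels. The gCV% and Cav errors are provisional. It would be too strong to call either a confirmed error, or to predict that fourfold Cav values or four-digit percent changes will be reported.

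A reader might also infer that trial conclusions are at risk. They are not. Safety endpoints, symptom scores, Cmax, AUC0-4h and the ANOVA tests do not change. The effect is limited to descriptive secondary PK/PD tables, so this should be corrected but is not critical. The sizes shown rest on assumed BLQ rates, log-scale SDs and illustrative values.

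**What to change.** 1. **BLQ rule, SAP 4.12.1.** Limit the zero substitution to the arithmetic statistics, median, minimum and maximum, and keep the existing NC rule. State one rule for geometric mean and gCV%. Either use non-BLQ values only, showing that n and footnoting that arithmetic and geometric means have different denominators (consistent with the figure rule), or report NC if any value is BLQ.
2. **Percent change, Table 4-2.** Rewrite the three rows as 100*(Day X - Day -1)/Day -1.
3. **Only if the source PDF shows the same text.** Write gCV% as 100*SQRT(exp(s^2) - 1), with s the SD of the logs, for every table reporting gCV% (SAP 4.12.1, 4.12.2, 4.12.4, 4.12.5). Write Cav as AUC0-4h / 4 h.

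SAP version 2.0 is final, so under SAP section 1 this goes into a Statistical Method Modification Form. The cost is a short rule with a footnote, three table rows and, conditionally, one formula and one more row. Data collection is unaffected.

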4.12.2 Pharmacokinetic Parameters

PK parameters will be provided by CPMS group. PK parameters will be calculated by NCA methods from the concentration-time data using Phoenix® WinNonlin® Version 8.3 or higher following these guidelines:

- Actual time from SC dosing will be used in the calculation of all derived pharmacokinetic parameters.
- There will be no imputation of missing data.
- Handling of BLQ samples for derivation of plasma PK parameters after single dose administration
 - BLQs at the beginning of a participant profile (i.e., before the first incidence of a measurable concentration) will be assigned to zero.
 - BLQs at the end of a participant profile (i.e., after the last incidence of a measurable concentration) will be set to missing.
 - Single BLQs which fall between two measurable concentrations will be set to missing.
 - Consecutive BLQs which fall between measurable concentrations will be set to missing. Measurable concentrations after consecutive BLQs will also be set to missing.
- Handling of BLQ samples for derivation of plasma PK parameters after multiple dose administration
 - BLQs for Day 1 at the beginning of a participant profile (i.e., before the first incidence of a measurable concentration) will be assigned to zero
 - BLQs on subsequent dosing days and not separated by a washout: pre-dose values, BLQs in the absorption phase, and BLQs between evaluable concentrations, will be substituted by LLOQ/2 before the calculation of the PK variables
 - Terminal BLQs (at the end of participant profile) will be set to missing.

Pharmacokinetic parameters will be estimated according to the guidelines presented in [Table 4-1](#).

Table 4-1 Pharmacokinetic Parameter and Estimation

Parameter	Guideline for Derivation
C_{max} , C_{min} , t_{max} , t_{min} , C_{trough} , C_{last} ,	Obtained directly from the observed concentration-time data
AUC_{last} (or AUC_{0-t})	
The AUC from zero time (pre-dose) to the time of last quantifiable concentration will be calculated by a combination of linear and logarithmic trapezoidal methods. Unless specifically requested and justified, the linear up/log down trapezoidal method will be employed.
 
The AUC_{0-t} is the sum of areas up to the time of the last quantifiable sample (no extrapolation will be applied):
 $AUC_{0-t} = \int_0^t C_{last} * dt$
AUC_{0-x}	
The AUC from zero time to the specific time x is the sum of areas up to the specific time x sample (no extrapolation will be applied):
 $AUC_{0-x} = AUC_{0-x} = \int_0^x C_x * dx$
AUC_{0-tau}	
The AUC over the dosing interval will be determined for multiple dose studies using the trapezoidal rule, as stated above. Calculated for days 1, 29 and 57.

AUC_{0-inf}	
The area from zero time extrapolated to infinite time will be calculated as follows:
 $AUC_{0-inf} = AUC_{0-t} + \frac{C_{last}}{\lambda_z}$ 
where C_{last} is the last observed quantifiable concentration. Calculated for days 1, 29, and 57.

$\%AUC_{ex}$	
The percentage of AUC_{0-inf} obtained by extrapolation will be calculated as follows:
 $\%AUC_{ex} = \frac{AUC_{0-inf} - AUC_{0-t}}{AUC_{0-inf}} \times 100$ 
Unless otherwise determined by PK Scientist's best knowledge and judgment, if the $\%AUC_{ex}$ is greater than 20% the value, $\%AUC_{ex}$, and all dependent parameters (i.e., AUC_{0-inf}, MRT, Vz and CL) will be flagged in listings and excluded from summary tables and statistical analysis of PK parameters. The reason for exclusion will be listed/footnoted in parameter listings.

λ_z and $t_{1/2}$	
 1. The apparent terminal phase rate-constant (λ_z) will be estimated by linear regression of concentration versus time data presented in a log-linear scale. 2. Data are primarily monotonically decreasing in magnitude and are representative of the actual decline in the log concentration-time curve. 3. Only those data points that are judged to describe the terminal log-linear decline will be used in the regression. 4. A minimum number of three data points in the terminal phase will be used in calculating λ_z with the line of regression starting at any post-C_{max} data point (C_{max} should not be part of the regression slope). Unless otherwise determined by PK Scientist's best knowledge and judgment or if instructed by the Sponsor, if the adjusted correlation coefficient (R^2 adjusted) is <0.9, then λ_z and all the λ_z dependent

Parameter	Guideline for Derivation
	
parameters (i.e. $t_{1/2}$, $AUC_{0-\infty}$, CL, MRT, and V_z) will be flagged in listings and excluded accordingly from summary tables and statistical analysis of PK parameters. The reason for exclusion will be listed/footnoted in parameter listings.
 
5. Unless otherwise determined by PK Scientist's best knowledge and judgment, the interval used to determine λ_z should be equal or greater than 1.5-fold the estimated $t_{1/2}$, and if less than 1.5-fold, λ_z will be flagged in listings and might be excluded from summary tables and statistical analysis of PK parameters. All the derived parameters (i.e. $t_{1/2}$, $AUC_{0-\infty}$, CL, MRT, and V_z) may also be flagged in listings and excluded from statistical analysis of PK parameters. The reason for exclusion will be listed/footnoted in parameter listings.
 
6. The $t_{1/2}$ will be calculated as follows:
 $t_{1/2} = \ln 2 / \lambda_z = 0.693 / \lambda_z$ 
7. Data points may be dropped from the linear regression if the PK Scientist considers the reported values to be anomalous. Any data points so designated should remain in the listings with a footnote and be identified in the study report with a rationale for exclusion.

CL or CL/F	
Apparent clearance (CL/F) following extravascular (e.g. SC) dosing will be calculated as:
 $CL/F = \frac{Dose}{AUC_{0-\tau}} / F$ 
In the case of steady state administration $AUC_{0-\tau}$ will be the denominator.

V_z/F	
Volume of distribution at terminal phase following extravascular (SC) dosing may be calculated from:
 $V_z/F = \frac{Dose}{\lambda_z \times AUC_{0-\tau}} / F = (CL/F) / \lambda_z$ 
Likewise, if derived for steady state administration $AUC_{0-\tau}$ will be used.

R_{ac}	
Accumulation ratio, calculated from comparison of single dose and steady state data:
 $R_{acAUC} = \frac{Steady\ state\ AUC_{0-\tau}}{Single\ dose\ AUC_{0-\tau}}$ $R_{acCmax} = Steady\ state\ C_{max} / Single\ dose\ C_{max}$ 
Day 1 represents single dose and day 57 represents steady state.

PK Parameters Listings:

PK parameters will be listed by participant for the SP. PK parameters that will be flagged and/or excluded from summary tables and statistical analyses of PK parameters will be flagged and footnoted with the reason for flagging/exclusion.

PK Parameter Summary Tables:

Biostatistics group will consider the derived PK parameters as source data and will use this data without rounding for calculation of PK parameters summary statistics tables.

PK parameters will be summarized by study day with descriptive statistics for the PKP.

Tabular summaries for PK parameters will report N (number of participants who received treatment) and n (number of participants with non-missing values).

Descriptive statistics for calculated PK parameters will include N, n, arithmetic mean, SD, CV%, geometric mean, gCV%, median, minimum, and maximum values. For t_{max} , only N, n, median, minimum, and maximum values will be presented. No descriptive statistics will be determined when fewer than three individual PK parameters are available.

The rules followed for presentation of PK parameters data with regards to the number of decimal places/significant digits for the listings of participant level PK parameters and summary tables of PK parameters are as follows:

PK Parameter Listings and Tables	Rounding
Derived Individual parameters	3 s.f.
Directly Derived Individual parameters (C _{max} , C ₁₂ , C ₂₄)	n s.f. as supplied by the analytical laboratory but not more than 3 s.f.
Minimum and Maximum	3 s.f.
Mean/SD/Median/Geomean	3 s.f.
CV%/gCV%	3 s.f.
Comparative estimates (e.g. ratios)	3 s.f.
CI and other percentages	2 d.p.
p-values	4 d.p.
N/n	Whole number
Exceptions for PK Tables	
t_{max} individuals and min/max	3 s.f.
t_{max} median only	3 s.f.

s.f = significant figures, d.p. = decimal place

